#### **11.1.3.1 Visit 6 (Day 15 [Week 2]; ±2 days)**

The following evaluations will be performed:

- Record vital signs.
- Record concomitant medications and therapies.
- Record adverse events.
- Take blood for safety laboratory testing.
- Collect urine for quantitative urinalysis at the central laboratory.
- Perform dipstick urinalysis.
- Compliance assessment for electronic diary.
- Check trial discontinuation criteria.

- Take blood for bone turnover marker evaluation.

#### **11.1.3.2        Visit 7 (Day 43 [Week 6]; ±3 days)**

The following evaluations will be performed:

- Record vital signs.
- Record concomitant medications and therapies.
- Record adverse events.
- Take blood for safety laboratory testing.
- Collect urine for quantitative urinalysis at the central laboratory.
- Perform dipstick urinalysis.
- Complete the assessment of the signs and symptoms of CRPS (for details, see Section 12.3.6).
- Compliance assessment for electronic diary.
- Check trial discontinuation criteria.
- Ask the subject to record the average, worst, and current pain on the tablet computer at the site.
- Measure edema, DMA, PPT, and AROM.
- Ask the subject to complete the PROMIS-29 profile and the PROMIS-EDDEP39 (the investigator should review the subject's answer to the PROMIS EDDEP39 question before the subject leaves the site and in case of suicidal ideation the investigator should consider involvement of a mental health professional).
- Ask the subject to complete the 6 neuropathic pain items of the SF-MPQ-2.
- Ask the subject to complete the PCS.
- Ask the subject to complete the PSEQ.
- Ask the subject to complete the PGI-S.
- Take blood for bone turnover marker evaluation.
- Ask the subject to complete the PGIC.

#### **11.1.3.3        Visit 8 (Day 85 [Week 12]; +7 days)**

Visit 8 must not occur prior to Day 85 in order for the subjects to have complete electronic diary data through Week 12 for the calculation of the primary endpoint.

The following evaluations will be performed:

- Record physical examination outcome (change from Visit 2).
- Record vital signs.
- Record concomitant medications and therapies.
- Record adverse events.
- Take blood for safety laboratory testing.
- Collect urine for quantitative urinalysis at the central laboratory.
- Perform dipstick urinalysis.

- Complete the assessment of the signs and symptoms of CRPS (for details, see Section 12.3.6).
- Training on electronic diary as, from Week 12, the electronic diary will ask for weekly assessments of pain intensity.
- Compliance assessment for electronic diary.
- Check trial discontinuation criteria.
- Ask the subject to record the average, worst, and current pain on the tablet computer at the site.
- Measure edema, DMA, PPT, and AROM.
- Ask the subject to complete the EQ-5D-5L.
- Ask the subject to complete the PROMIS-29 profile and the PROMIS-EDDEP39 (the investigator should review the subject's answer to the PROMIS EDDEP39 question before the subject leaves the site and in case of suicidal ideation the investigator should consider involvement of a mental health professional).
- Ask the subject to complete the 6 neuropathic pain items of the SF-MPQ-2.
- Ask the subject to complete the PCS.
- Ask the subject to complete the PSEQ.
- Ask the subject to complete the PGI-S.
- Ask the subject to complete the WPAI: CRPS (US sites only).
- Collect information for medical resources utilization and health economics (US sites only).
- Take blood for bone turnover marker evaluation.
- Take blood for sIL-2R testing.
- Take blood for omics testing.
- Ask the subject to complete the PGIC.

#### **11.1.3.4        Visit 9 (Day 113 [Week 16]; ±4 days)**

The following evaluations will be performed:

- Record vital signs.
- Record concomitant medications and therapies.
- Record adverse events.
- Complete the assessment of the signs and symptoms of CRPS (for details, see Section 12.3.6).
- Compliance assessment for electronic diary.
- Check trial discontinuation criteria.
- Ask the subject to record the average, worst, and current pain on the tablet computer at the site.
- Ask the subject to complete the pain intensity question (question number 29, GLOBAL07) of the PROMIS-29 profile.
- Ask the subject to complete the PGI-S.

- Ask the subject to complete the PGIC.

#### **11.1.3.5      Visit 10 (Day 155 [Week 22]; ±4 days)**

The following evaluations will be performed:

- Record vital signs.
- Record triplicate 12-lead ECG.
- Record concomitant medications and therapies.
- Record adverse events.
- Take blood for safety laboratory testing.
- Collect urine for quantitative urinalysis at the central laboratory.
- Perform dipstick urinalysis.
- Perform a urine β-HCG pregnancy test.
- Complete the assessment of the signs and symptoms of CRPS (for details, see Section 12.3.6).
- Compliance assessment for electronic diary.
- Check trial discontinuation criteria.
- Ask the subject to record the average, worst, and current pain on the tablet computer at the site.
- Ask the subject to complete the pain intensity question (question number 29, GLOBAL07) of the PROMIS-29 profile.
- Ask the subject to complete the PGI-S.
- Take blood for bone turnover marker evaluation.
- Ask the subject to complete the PGIC.

#### **11.1.4      Follow-up Period 2**

##### **11.1.4.1      Visit 11 (Day 183 [Week 26]; +7 days)**

Visit 11 must not occur prior to Day 183, to ensure a full 6 months of follow-up for all subjects.

If Visit 11 is not performed on Day 183, Visit 12 to Visit 15 should proceed in accordance with the originally scheduled time windows relative to Visit 11.

The following evaluations will be performed for all subjects:

- Record physical examination outcome (change from Visit 8).
- Record body weight.
- Record vital signs.
- Record concomitant medications and therapies.
- Assess further need of concomitant treatment for CRPS (in particular opioids), including decreases in dose or frequency as applicable.
- Record adverse events.
- Take blood for safety laboratory testing.

- Collect urine for quantitative urinalysis at the central laboratory.
- Perform dipstick urinalysis.
- Compliance assessment for electronic diary.
- Check trial discontinuation criteria (for details, see Section 9.3.1).
- Ask the subject to record the average, worst, and current pain on the tablet computer at the site.
- Measure edema, DMA, PPT, and AROM.
- Ask the subject to complete the EQ-5D-5L.
- Ask the subject to complete the PROMIS-29 profile and the PROMIS-EDDEP39 (the investigator should review the subject's answer to the PROMIS EDDEP39 question before the subject leaves the site and in case of suicidal ideation the investigator should consider involvement of a mental health professional).
- Ask the subject to complete the 6 neuropathic questions of the SF-MPQ-2.
- Ask the subject to complete the PCS.
- Ask the subject to complete the PSEQ.
- Ask the subject to complete the PGI-S.
- Ask the subject to complete the WPAI: CRPS (US sites only).
- Collect information for medical resources utilization and health economics (US sites only).
- Take blood for sIL-2R testing.
- Take blood for omics testing.
- Ask the subject to complete the PGIC.
- Check the criteria to continue into Treatment Period B.

#### **Decision to go into Treatment Period B**

Compliance with the criteria to continue into Treatment Period B must be confirmed before allocation to IMP. The pain intensity question (question number 29, GLOBAL07) of the PROMIS-29 profile has to have a value of at least 4 at Visit 11. Subjects who do not meet the criteria to continue into Treatment Period B will continue with the Follow-up Period 2.

##### **11.1.4.1.1 Subjects meeting the criteria to continue into Treatment Period B**

For subjects continuing into Treatment Period B, the following evaluations will be performed prior to the start of IMP infusion:

- Record triplicate 12-lead ECG (at least 15 minutes prior to the start of infusion).
- Perform semi-quantitative dipstick urinalysis for urinary ACR.
- Perform a urine  $\beta$ -HCG pregnancy test.
- Perform urine drugs of abuse testing.
- Complete the assessment of the signs and symptoms of CRPS (for details, see Section 12.3.6).
- Check IMP suspension criteria (for details, see Section 9.3.2).

Once the above evaluations have been performed, the subject will be re-allocated to IMP using the interactive response technology system and the IMP will be administered (for details, see Section 10.2).

The following evaluations will be performed after the infusion:

- Record vital signs.
- Record triplicate 12-lead ECG (at least 15 minutes after the infusion).
- Record adverse events.

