**Other data to be collected that are not directly attributed to or considered as an endpoint**

---

General note: All efficacy and safety data evaluated during Treatment Period B and Follow-up Period 2 will be analyzed descriptively separately for subjects who are treated in Treatment Period B and subjects who are not treated. For subjects treated in Treatment Period B, analyses will be performed for subjects initially treated with placebo and subjects initially treated with neridronic acid.

All efficacy assessments will be evaluated for the time points indicated in the schedules of events.

*To assess the efficacy of neridronic acid in subjects with CRPS*

- Change from baseline in average pain intensity recorded on the tablet computer.
- Change from Week 26 in average pain intensity recorded on the tablet computer.
- Pain response to treatment, defined as at least 50% decrease from baseline in the average pain intensity, based on pain intensity recordings on the tablet computer.
- Pain response to treatment, defined as at least 50% decrease from Week 26 in the average pain intensity, based on pain intensity recordings on the tablet computer.
- Pain response to treatment, defined as at least 30% decrease from baseline in the average pain intensity, based on pain intensity recordings on the tablet computer.
- Pain response to treatment, defined as at least 30% decrease from Week 26 in the average pain intensity, based on pain intensity recordings on the tablet computer.
- Change from baseline in pain intensity scores determined using worst and current pain ratings recorded daily in the electronic diary.
- Change from baseline in worst and current pain intensity ratings, recorded on the tablet computer.
- Change from Week 26 in worst and current pain intensity ratings, recorded on the tablet computer.
- Duration of effect based on average pain intensity recordings in the electronic diary.
- Change from baseline in the pain intensity level of DMA.
- Change from baseline in PPT ratios.
- Change from baseline in the ratio of the figure of eight measurements of the affected limb versus the unaffected limb.
- Change from baseline in the active range of motion (AROM) ratio (affected limb and unaffected limb) measured in the hand or foot, respectively.
- Change from baseline in the CRPS Severity Score.
- Patient Global Impression of Change (PGIC).
- Patient Global Impression of Severity (PGI-S).

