### **1.3.3 Criteria to continue into Treatment Period B**

Safety laboratory tests will be taken at Visit 10. In case the serum calcium and/or vitamin D levels meet the exclusion criteria to continue into Treatment Period B, additional supplementation similar to the Enrollment Period is allowed between Visit 10 and Visit 11. In case of any safety laboratory retesting, the scheduling and time window of Visit 11 must not be affected.

The decision regarding whether a subject will continue into Treatment Period B will be taken at Visit 11, based on the following criteria:

- A value of at least 4 on the pain intensity question (question number 29, GLOBAL07) of the PROMIS-29 profile at Visit 11.
- The following exclusion criteria are not met:
  - Evidence of severe renal impairment (eGFR less than 30 mL/min/1.73 m^2 using the 2009 CKD-EPI creatinine equation [Levey et al. 2009] or a urinary ACR greater than 150 mg/g), based on central safety laboratory data obtained prior to Visit 11. A single repeat laboratory test is allowed.
  - Corrected QT interval (QTcF) greater than 470 ms (average of 3 ECGs obtained at Visit 10) according to the central ECG reading facility evaluation or QTcF greater than 470 ms at pre-dose ECG at Visit 11 according to the investigator's judgment; serum potassium outside the central laboratory's reference range at Visit 10 (a single repeat laboratory test is allowed); clinically unstable cardiac disease, including: unstable atrial fibrillation, symptomatic bradycardia, unstable congestive heart failure, active myocardial ischemia, or an indwelling pacemaker; evidence of complete left bundle branch block; complete atrioventricular block; any other known risk factor for torsade de pointes.
  - Subjects receiving medications with a known risk of torsades de pointes within 7 days prior to re-allocation.
  - Subjects taking forbidden concomitant medications/therapies or not being able to follow the rules of use of concomitant treatment (see Section [1.4.2](#)).
  - Recent tooth extraction or other invasive dental procedure (within 3 months prior to Visit 11), unhealed or infected extraction site, or significant dental/periodontal disease (e.g., impacted molars, severe tooth decay, foci of infection) that may pre-dispose to need for tooth extraction or other invasive dental procedures during the further course of the trial.

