		Additional visits only for subjects going into Treatment Period B					
	Visit 11 a	Visit 12 b	Visit 13 b	Visit 14 b	Visit 15 r	Visit 16	Visit 17 c
	Day 183/ Week 26 (+7 days)	Day 186 (±1 day)	Day 189 (±1 day)	Day 192 (±1 day)	Day 197/ Week 28 (+7/-2 days)	Day 253/ Week 36 (±7 days)	Day 365/ Week 52 (+7 days)
Record physical examination outcome d	X						X
Record body weight	X						X
Record vital signs e	X	X	X	X	X	X	X
Record 12-lead ECG f	X r	X	X	X	X		X
Record concomitant medications and therapies g	X	X	X	X	X	X	X
Assess further need of concomitant treatment for CRPS (in particular opioids), including decreases in dose or frequency as applicable	X					X	
Record adverse events h	X	X	X	X	X	X	X
Take blood for safety laboratory testing	X	X	X	X	X	X	X
Collect urine for quantitative urinalysis at the central laboratory	X	X	X	X	X	X	X
Perform dipstick urinalysis	X	X	X	X	X	X	X

Trial procedure	Follow-up Period 2						
	Treatment Period B (only subjects meeting the criteria to continue into Treatment Period B)						
			Additional visits only for subjects going into Treatment Period B				
	Visit 11 a	Visit 12 b	Visit 13 b	Visit 14 b	Visit 15 r	Visit 16	Visit 17 c
	Day 183/ Week 26 (+7 days)	Day 186 (±1 day)	Day 189 (±1 day)	Day 192 (±1 day)	Day 197/ Week 28 (+7/-2 days)	Day 253/ Week 36 (±7 days)	Day 365/ Week 52 (+7 days)
	Perform semi-quantitative dipstick urinalysis for urinary ACR	X r	X	X	X		
	Perform a urine β-HCG pregnancy test i	X r	X	X	X		X
Perform urine drugs of abuse testing	X r						
Complete the assessment of the signs and symptoms of CRPS j	X r					X	X
Re-allocate to IMP k	X r						
Check trial discontinuation criteria	X	X	X	X	X	X	
Check IMP suspension criteria l	X r	X	X	X			
Administer IMP m	X r	X	X	X			
Ask the subject to record the average, worst, and current pain on the tablet computer at the site q	X q	X	X	X	X	X	X
Measure edema, DMA, PPT, and AROM s	X					X	X
Ask the subject to complete the EQ-5D-5L	X					X	X

Trial procedure	Follow-up Period 2						
	Treatment Period B (only subjects meeting the criteria to continue into Treatment Period B)						

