- m) All measurements (including blood sampling for hematology, clinical chemistry, urinalysis; ECG; vital signs; physical examination) must be completed before the start of the first infusion of IMP. Investigational medicinal product must be diluted in 500 mL saline and administered by slow intravenous infusion (the infusion time must be at least 240 minutes [up to a maximum of 260 minutes]).
- n) At US sites only.
- o) Blood samples for bone turnover markers (C-terminal telopeptide of type I collagen, bone alkaline phosphatase, and procollagen type I amino-terminal propeptide) should be obtained in the morning after an overnight fast.
- p) Compliance with the criteria to continue into Treatment Period B must be confirmed before allocation to IMP. The pain intensity question (question number 29, GLOBAL07) of the PROMIS-29 profile has to have a value of at least 4 at Visit 11. Subjects who do not meet the criteria to continue into Treatment Period B will continue with the Follow-up Period 2.
- q) Worst and average pain intensity ratings will be based on a 24-hour recall period.
- r) Only for the subjects going into Treatment Period B.
- s) Edema will only be measured in subjects reporting asymmetric edema as part of the assessment of the signs and symptoms of CRPS at baseline (Visit 2). The AROM will only be measured in subjects reporting decreased AROM as part of the assessment of the signs and symptoms of CRPS at baseline (Visit 2).
- t) The blood sample for omics testing will be collected in consenting subjects.
- u) No training needed at Visit 17.

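### At Visit 11 (Week 26) the CRPS Severity Score is collected only in subjects entering Treatment Period B, so its planned Week 26 summary by arm is conditioned on post-randomization pain

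*Protocol*

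**What the plan says.** Protocol Section 11.1.4.1 gives a list of Visit 11 evaluations for all subjects. It includes edema, DMA, PPT, AROM and the questionnaires, but not the signs and symptoms assessment. That assessment appears only in Section 11.1.4.1.1, under the opening "For subjects continuing into Treatment Period B, the following evaluations will be performed prior to the start of IMP infusion".

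The schedule in Section 1.6.2 agrees. In the row "Complete the assessment of the signs and symptoms of CRPS" the Visit 11 cell carries footnote r, "Only for the subjects going into Treatment Period B", while the cells for Visits 16 and 17 carry no restriction.

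The entry rule in Section 1.3.3 is "A value of at least 4 on the pain intensity question (question number 29, GLOBAL07) of the PROMIS-29 profile at Visit 11", together with renal, ECG, laboratory, dental and medication criteria.

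Section 12.3.6 derives the 0 to 16 CRPS Severity Score from this assessment. Section 1.2 lists "Change from baseline in the CRPS Severity Score" among the other efficacy data and adds: "All efficacy assessments will be evaluated for the time points indicated in the schedules of events". Section 1.5.3 has such data summarized descriptively in the Full Analysis Set, and Section 14.1.2 has analyses done by treatment group.

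**The concern.** Whether a subject has a Week 26 score depends on pain measured at that visit. Pain is what the treatment is meant to lower, so the subset with a score is defined by a post-randomization outcome and need not be comparable between arms. Followed exactly, the protocol cannot deliver a Full Analysis Set summary of this score at Week 26.

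Week 26 is the time point of the 26-week report (Section 1.5) and the last visit before open-label retreatment. After it, subjects first given placebo may receive neridronic acid, so later visits no longer give a clean comparison of the randomized arms. A Week 26 score that was not collected cannot be recovered in the analysis.

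**Working it through.** **Do the passages agree?** Yes. The all-subjects list omits the item, the Period B list contains it, and footnote r restricts the cell. This is a fixed feature of the plan and not a table misread. From Visit 2 on, the assessment is listed without restriction at Visits 2, 7, 8, 9, 10, 16 and 17 (Sections 11.1.2 to 11.1.4), so Visit 11 is the only restricted one.

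**Direction.** Section 12.9 reports a strong correlation between changes in the score and changes in pain, without a coefficient. If active treatment lowers pain, more active subjects fall below 4 and go unscored. With a positive correlation these tend to be subjects with low scores, so the mean of the scored active subjects rises by more than that of the scored placebo subjects.

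**Inputs from the protocol.** Section 1.5.1 gives a pain difference of 1.0 and an SD of 2.0. Its sample size reproduces: a two-sample t-test at one-sided 2.5% and 90% power needs 85.03, rounded up to 86 per arm. The plan allocates 90 per arm. It gives no figure for the severity score, and the 1.0 is its Week 12 diary assumption, borrowed here for Week 26.

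**Assumed inputs.** Week 26 pain means 5.5 (placebo) and 4.5 (active); score SD 3; true score difference 1.5; within-arm correlation ρ between pain and score of 0.3, 0.5 or 0.7.

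**Closed form.** Pain is a whole number, so at least 4 corresponds to at least 3.5 on a continuous scale.

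- Share scored = Φ((mean − 3.5)/2): placebo Φ(1.0) = 84%, active Φ(0.5) = 69%.
- Rise in mean pain among those scored = 2·φ(z)/Φ(z): placebo 0.575, active 1.018, a gap of 0.443.
- Loss in score difference = ρ × (3/2) × 0.443 = 0.20, 0.33 and 0.47 points for ρ = 0.3, 0.5 and 0.7.
- As a share of 1.5: 13%, 22% and 31%.

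A simulation with rounded, clipped scales gives the same picture: a difference of 1.49 among all subjects becomes 1.29, 1.16 and 1.02 among those scored. With pain means of 4.5 and 3.5 (69% and 50% scored), 1.48 becomes 1.22, 1.05 and 0.88, a loss of 18% to 41%.

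**Wider range.** A second simulation took baseline pain of at least 4 with mean 5.5 to 7.5 (SD 1.5), a placebo pain change of −1 to −2, a pain effect of −1.0 (SD 2.0), score SD 3 and ρ from 0.3 to 0.7. It applied the pain rule only.

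| Quantity | Result |
|---|---|
| Placebo subjects scored | 57% to 89% |
| Active subjects scored | 40% to 78% |
| Unscored, of 180 | about 30 to 93 |
| True −1.0 seen as | −0.87 to −0.52 (12% to 48% lost) |
| True −1.5 seen as | −1.38 to −1.03 (8% to 32% lost) |

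With ρ = 0 nothing is lost. With no effect on pain or score, both arms keep 75% and the difference stays at zero.

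**The case against.** The strongest reply is that little depends on this score. Section 1.2 lists it among data not considered an endpoint, it is only described, and the confirmatory family in Section 1.5.3.4 does not contain it. No Week 26 test of the arms is planned for it. That stands, and it limits the importance of the point.

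Second, scores not selected on pain are nearby: Weeks 6, 12, 16 and 22 before Week 26, and Weeks 36 and 52 after it. At Week 26 itself all subjects still provide pain ratings, PGI-S, PGIC, PROMIS-29, DMA and PPT. This also stands, but Week 22 is not Week 26, and Weeks 36 and 52 follow retreatment.

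Third, Section 1.6.2 places Visit 11 under Follow-up Period 2, whose data are summarized separately for retreated and other subjects. The score could then be read as a pre-retreatment value for the Period B cohort. The wording does not settle this, since Section 1.1.2 runs Follow-up Period 1 up to Visit 11. On either reading, separate reporting cannot supply values that were never collected.

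Fourth, the assumed bias is small beside sampling error. With about 76 and 62 subjects scored (90 × 0.84 and 90 × 0.69), the standard error of the difference is 3 × √(1/76 + 1/62) ≈ 0.51, against a loss of 0.20 to 0.47. That is fair for those inputs, but the loss is systematic and avoidable.

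A reader might go further than the documents allow in three ways:

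- That every good responder is lost, leaving only non-responders. Entry uses an absolute rating, not a response. If the pain ratings agree, a subject who falls from 8 to 4 is a 50% responder and is still scored, while some subjects with pain of at least 4 fail a safety criterion and are not.
- That subjects not retreated lack a Week 26 reference for Weeks 36 and 52. Section 1.2 plans change from Week 26 for tablet pain and EQ-5D-5L, but for this score only change from baseline.
- That the restriction was an oversight. Text and table agree, which fits a deliberate choice equally well.

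**Conclusion.** The point holds as a gap in one descriptive efficacy outcome at one visit. The protocol asks for a Full Analysis Set summary by arm at each scheduled time point, yet at Week 26 collects the score only in subjects with residual pain of at least 4 who also pass the safety criteria.

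That the summary is conditioned on a post-randomization outcome follows from the text alone. Attenuation is conditional: it needs a real effect on pain and a positive correlation between score and pain. Section 12.9 supports the correlation, but nothing in the protocol fixes its size. The range of about 8% to 48% is an illustration, not a forecast. The change is worth making because it is cheap and the missing values cannot be recovered later.

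**What to change.** In Section 1.6.2, remove footnote r from the Visit 11 cell of the row "Complete the assessment of the signs and symptoms of CRPS". Move the same item from Section 11.1.4.1.1 to the all-subjects list in Section 11.1.4.1, and have it completed before the Period B decision. In the simulations the attenuation then disappears, and the Week 26 denominator rises from about 87 to 150 up to 180, before dropout.

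The cost is two wording changes and one short extra examination in subjects who do not continue. They attend Visit 11 anyway, and sites already do this examination at seven other visits. If the change cannot be made, drop the Week 26 summary of this score by arm and use Week 22 (Visit 10) as the last summary before retreatment that is not selected on pain.
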